The overall objectives of this research project are to prospectively investigate ICU day-night light patterns and their association with circadian abnormalities; investigate the association between circadian abnormalities and the duration of delirium; and evaluate the feasibility of providing daytime bright light to treat circadian abnormalities among critically ill patients. Our central hypothesis is that exposure to abnormally high overnight light and abnormally low daytime light (non-circadian light patterns) disrupts the circadian master clock and causes circadian abnormalities in ICU patients. In turn, circadian abnormalities contribute to sleep disruption and ultimately ICU delirium. The rationale for the proposed project is that circadian abnormalities may constitute a novel therapeutic target for interventions to prevent or shorten delirium and improve ICU outcomes. This work builds upon our own work and published studies that describe circadian abnormalities in critically ill patients. Prior studies are limited by small numbers of subjects or by periods of observation that start many days after ICU admission.¹⁷⁻²³ We will use a melatonin metabolite, urinary 6-sulfatoxymelatonin (aMT6s), to measure circadian abnormalities; this measure has been successfully used in critically ill patients.²⁴ We plan to accomplish our overall objectives via the following specific aims:

Aim 1: Determine the association between ICU day-night light patterns and circadian abnormalities (i.e., circadian misalignment and decreased circadian amplitude).

Hypothesis 1: Non-circadian ICU light patterns (i.e., abnormally low daytime light levels and abnormally high overnight light levels) are associated with increased circadian misalignment and decreased circadian amplitude as measured by urinary aMT6s.

Aim 2: Determine the association between circadian abnormalities and the duration of delirium.

Hypothesis 2: Increased circadian misalignment and decreased circadian amplitude are associated with more days of delirium.

Aim 3: Evaluate the feasibility of providing daytime bright light in the ICU and examine the effect size of daytime bright light on circadian abnormalities in a pilot randomized controlled trial.

[figure not shown]
Hypothesis 3.1: Daytime bright light is acceptable and tolerable to patients and has high fidelity and sustainability as an intervention.

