The circadian system is controlled by a central master clock and is a key determinant of sleep timing. The master clock is synchronized with the 24-hour day by external cues via a process called entrainment. Light is the most influential external entrainment cue. Under normal entrainment, the circadian system promotes arousal during the day and allows sleep during the night. Sleep quality and length are optimal when they occur during an individual's "biologic" or "circadian" night. Circadian abnormalities contribute to inappropriate sleep timing, impaired sleep quality and decreased sleep quantity. These three elements of sleep disruption have been clearly shown in critically ill patients,¹⁵⁻¹⁷ and together with circadian abnormalities these elements form a vicious cycle. Circadian abnormalities are defined in this proposal as misalignment and decreased amplitude. We assert that optimal sleep promotion and therefore optimal treatment and prevention of delirium requires the promotion of normal circadian entrainment. The proposed project supports this by investigating the influence of ICU day-night light patterns on circadian abnormalities, examining the association between circadian abnormalities and duration of delirium and piloting a daytime bright light intervention (Figure 1).

Premise for Aims 1 and 2: ICU day-night light patterns conflict with circadian entrainment and cause circadian abnormalities. External cues for entrainment include light, meal schedule, and physical activity. As noted above, light has by far the greatest biologic influence on entrainment.¹⁸ The robustness of entrainment and vulnerability to disruption are determined by the timing, intensity (lux), and duration of a light dose.¹⁹ Normal entrainment requires bright light exposure during the day (wake) period and dim or no light during the night (sleep) period. Daytime bright light interventions deliver at least 1,000 lux and more typically deliver 2,500 to 10,000 lux over 30 minutes to several hours.^{20, 21} During the night, short bursts of bright light (e.g., 5 minutes) at relatively lower intensities (e.g., 100 or 250 lux) can cause circadian abnormalities.¹⁹ Interventions aimed at ICU sleep promotion have focused on lowering overnight

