light levels,²² but have not addressed the significant problem of daytime light being too low for entrainment (See preliminary data). *It is our premise in Aim 1 that non-circadian day-night light patterns in the ICU cause circadian abnormalities. Circadian abnormalities are present in critical illness, associated with delirium, and feasible to study.* Studies of urinary 6-sulfatoxymelatonin (aMT6s), continuous heart rate, and actigraphic rest-activity have shown associations between critical illness and circadian abnormalities.²³⁻²⁸ In these studies, roughly 75% of ICU patients studied have evidence of circadian abnormalities. One small study has shown that delirium is associated with circadian misalignment in patients weaning from mechanical ventilation.²⁹ These studies (Table 1) demonstrate the feasibility of studying circadian rhythms in the ICU but have been limited by small numbers (<30 patients), brief periods of observation (24 hours), or periods of observation that start days after ICU admission (>5 days post admission). *It is our premise in Aim 2 that circadian abnormalities are common in ICU patients and likely to be associated with duration of delirium. Delirium is at least partially mediated by sleep disruption, which is a proposed factor on the causal pathway between circadian abnormality and delirium.*

Table 1: Circadian Rhythm Measurements and Related ICU Studies

Variable	Strengths	ICU Studies Using this Variable
Urinary 6-aMT6s	Gold Standard	Septic patients (n=17) v. non-septic ICU (n=7) and healthy controls (n=21); enrollment 11 days post ICU admission; abnormal aMT6s patterns in septic patients but not controls. ²⁷ Additional References: Gehlbach, ³⁰ Frisk ²⁴ Verceles ²⁸
Heart rate	Recorded as part of usual care; starts at ICU admission	Medical ICU sedated patients (N=11); time post ICU admission not listed; heart rate with circadian variability but misaligned. ³¹
Actigraphy	Low cost for long-term monitoring; non-invasive	Neurologic ICU with traumatic brain injury patients (N=16); enrollment 18 days post injury; rest-activity consolidation associated with better recovery. ³²

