Expected Outcomes: We expect that a low day/night dose ratio will be associated with increased misalignment and decreased amplitude of urinary aMT6s. We expect that this relationship will remain after controlling for listed confounders. We anticipate that we will see effect modification by sepsis and by OSA risk.

Aim 2: Determine the association between circadian abnormalities and the duration of delirium.

Rationale: Aim 2 will test our hypothesis that increased circadian misalignment and decreased amplitude are associated with more days of delirium. Our approach is to measure days of delirium in the same cohort of 100 patients that have been evaluated for circadian abnormalities in Aim 1. After enrollment, we will check patients twice daily for delirium until hospital discharge. We have selected days of delirium as our metric of delirium severity because it is standard in the field and because studies have shown that additional days of delirium convey additional risk for mortality and cognitive impairment.^{4, 5} We will measure (and control for) total amount of sleep (sleep quantity) and overnight sleep efficiency (sleep quality) via actigraphy. We propose that these metrics of sleep disruption act as potential confounders and/or effect modifiers of the association between circadian abnormalities and delirium. For this project focused upon circadian patterns and sleep disruption rather than detailed sleep architecture (e.g., sleep stages), actigraphy, rather than polysomnography, is the sleep measure of choice. It is our expectation that circadian abnormalities will be associated with increased days of delirium. *This aim will be the basis for investigation of circadian entrainment as a means of treating ICU delirium.*

Research Design: The 100 subjects enrolled in Aim 1 will be examined for the outcome of days of delirium in Aim 2. We will collect the following measures: Circadian measures, actigraphy, and patient characteristics will be collected as described in Aim 1. Delirium: Research staff blinded to patient circadian

status and trained in the CAM-ICU will assess patients for delirium once daily from the time of MICU admission until hospital discharge or hospital day 30.⁴⁸ The CAM-ICU is a guideline recommended, validated delirium detection tool with a sensitivity >93% and a specificity >98%.^{2, 48, 49} We are increasing sensitivity in our study by adding validated daily chart review for delirium.⁵⁰

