Aim 2 Analytic Approach: Circadian measures will be analyzed as in Aim 1. Sleep disruption will include two measures: (1) total amount of sleep, a continuous variable calculated as the number of sleep epochs in a 24 hour period and (2) overnight sleep efficiency, a continuous variable calculated as the percent of epochs scored as sleep between 22:00 and 06:00. Sleep will be based on standard Philips Actiwatch Software algorithms. Days of Delirium will be calculated as the sum of days on which the patient is delirious. Delirium will be considered present if either the CAM-ICU or the chart abstraction is positive for a given calendar day. Patients will be censored at day 30 or at hospital discharge.^{59, 60} Confounder and effect mediator variables: Severity of illness, age, and gender will be treated as in Aim 1. Ventilator use will include invasive and noninvasive positive pressure ventilation and will be quantified as ventilator-free days based on published algorithms.⁶¹ For sedative-hypnotic medications, equivalent daily doses of benzodiazepines and narcotics will be calculated using published algorithms.^{62, 63} Propofol and dexmedetomidine total daily dose will be recorded and included in the models.

Testing for Associations: Multivariable Poisson models will assess the associations between circadian misalignment and amplitude and days of delirium. Models will be adjusted for age, severity of illness, ventilator-free days, dose of sedative medication, and measures of sleep disruption. We will test for modification of the associations between misalignment and amplitude and days of delirium by age, sedative-hypnotic medication dose and measures of sleep disruption. Linearity, serial correlation, and model fit will be addressed as in Aim 1. **Power Calculation:** Patients with delirium on the day of enrollment will be excluded, our effective sample size will be reduced by 20% to 80 participants. Assuming two-sided alpha of 0.05, 90% power, overdispersion of 20%, and a mean of 3 days of delirium,⁴ our sample of 80 allows the detection of a minimal risk ratio of 1.12 for each 60 minutes of misalignment. Under the same assumptions, our sample of 80 will detect a minimal risk ratio of 1.08 for each change of 100ng of aMT6s.⁶⁴

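### The only specified Aim 2 delirium model adjusts for sleep disruption, which the protocol itself places on the pathway to delirium, so it cannot by itself test Hypothesis 2 as stated

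*Combined protocol and SAP*

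**What the plan says.** The combined protocol and SAP gives sleep disruption several different roles.

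- **Mediator.** The central hypothesis in the opening statement of objectives says: "In turn, circadian abnormalities contribute to sleep disruption and ultimately ICU delirium". The Background section on the premise for Aims 1 and 2 is more explicit: "Delirium is at least partially mediated by sleep disruption, which is a proposed factor on the causal pathway between circadian abnormality and delirium".
- **Possible two-way relation.** The Background also says of the elements of sleep disruption that "together with circadian abnormalities these elements form a vicious cycle".
- **Confounder or modifier.** The Aim 2 Rationale says: "We will measure (and control for) total amount of sleep (sleep quantity) and overnight sleep efficiency (sleep quality) via actigraphy". It continues: "We propose that these metrics of sleep disruption act as potential confounders and/or effect modifiers of the association between circadian abnormalities and delirium".
- **Modifier, and absent from the list of controls.** Aim 2, Expected Outcomes, expects the association to survive control for age, gender, severity of illness and ventilator-free days. Sleep is not in that list and appears separately as an expected effect modifier.
- **Adjustment variable.** Statistical Considerations, Aim 2, Testing for Associations, specifies the model: "Models will be adjusted for age, severity of illness, ventilator-free days, dose of sedative medication, and measures of sleep disruption". Interactions with sleep are to be tested as well. The covariate heading just above uses the term effect mediator, although the sleep measures are defined before that heading and not under it.

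The target is Hypothesis 2: "Increased circadian misalignment and decreased circadian amplitude are associated with more days of delirium". The Aim 2 Rationale says what the result is for: "This aim will be the basis for investigation of circadian entrainment as a means of treating ICU delirium". No Aim 2 model without sleep, no sequential adjustment and no mediation analysis is specified.

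**The concern.** Adjusting for a variable that carries part of an effect removes that part from the coefficient. If the premise is right, the planned model discards the route that motivates the work, and what remains answers a narrower question than Hypothesis 2 asks. A small or non-significant coefficient could then mean either that circadian abnormality does not matter for delirium, or that it matters chiefly by disrupting sleep. The planned analysis cannot tell these apart, and a programme on circadian entrainment is to rest on it. If a sleep-free model is added only after the data are seen, choosing between the two becomes data-driven.

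**Working it through.** **The plan's own figures.** The Aim 2 power statement gives minimal detectable risk ratios of 1.12 per 60 minutes of misalignment and 1.08 per 100 ng of aMT6s. Its inputs are N = 80, two-sided alpha 0.05, 90% power, a mean of 3 days and 20% overdispersion. No Aim 2 standard deviation is given, so I used the Aim 1 values of 95 minutes and 180 ng:

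RR = exp[(1.960 + 1.282) × √(1.2 / (80 × 3 × SD²))]

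- Misalignment, SD = 95/60 units: exp(3.2415 × 0.04466) = 1.156, against 1.12 stated.
- Amplitude, SD = 180/100 units: exp(3.2415 × 0.03928) = 1.136, against 1.08 stated.

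The stated figures do not reproduce on these inputs. That is a separate matter. Here 1.12 and 1.08 serve only as reference values, and the argument does not depend on them.

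**Mediation only.** Let m be the share of the log risk ratio that runs through sleep. The documents give no value, so 25%, 50% and 75% are assumptions. Without sleep terms the model recovers the overall RR. With them it recovers RR^(1−m).

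| m (assumed) | from 1.12 per 60 min | from 1.08 per 100 ng |
|---|---|---|
| 25% | exp(0.75 × 0.1133) = 1.089 | 1.059 |
| 50% | exp(0.50 × 0.1133) = 1.058 | 1.039 |
| 75% | exp(0.25 × 0.1133) = 1.029 | 1.019 |

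These figures restate the assumed shares and are not evidence about them. If power were 90% for the overall effect, power for the sleep-adjusted coefficient would be Φ[3.2415(1−m) − 1.960] = 68%, 37% and 12.5%, before any loss from collinearity.

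**Mediation plus confounding.** Assume that later sleep disruption = 0.3 × standardised misalignment + 0.5 × earlier sleep disruption + noise (SD 0.8). Earlier sleep correlates r with misalignment, and delirium depends only on misalignment and later sleep. All of these are assumptions. With a true overall RR of 1.12, the sleep-free model gives

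ln RR = ln 1.12 × (1 + m × r × 0.5/0.3)

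| r | m = 25% | m = 50% | m = 75% |
|---|---|---|---|
| 0.1 | 1.125 | 1.131 | 1.136 |
| 0.3 | 1.136 | 1.152 | 1.169 |
| 0.5 | 1.147 | 1.174 | 1.202 |

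The sleep-adjusted model still gives 1.089, 1.058 and 1.029. Simulated Poisson fits with 200,000 subjects agree to within about 0.003. Here the sleep-free estimate is too high and the sleep-adjusted one too low. At m = 75% and r = 0.5 the sleep-free log RR is inflated by 0.75 × 0.5 × 0.5/0.3 = 62.5%, while the sleep-adjusted log RR is 75% too small. The ratio of the two errors is 0.5r/0.3, so above r = 0.6 the sleep-free model is the worse of the two. The other planned covariates were not modelled.

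**Timing.** Urinary aMT6s is collected for up to 72 hours from enrolment. Actigraphy runs from Day 1 to at least Day 5 unless the patient leaves hospital. The two windows overlap, and no ordering of the sleep measure before or after the circadian measure is specified.

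**The case against.** The strongest reply is that sleep may truly confound. The Aim 2 Rationale says so openly, and the Background describes a two-way relation. Whether circadian abnormality matters beyond poor sleep is a legitimate question. If sleep only mediates, adjustment is conservative, and a positive result would still support Hypothesis 2. The hypothesis speaks of association and does not name a total effect. The Expected Outcomes list also omits sleep, so one could say that a sleep-free comparison is in view.

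Much of this stands. It rules out simply deleting sleep, and under the assumed paths a sleep-free estimate can be badly inflated. It does not rescue the plan as written. When sleep both mediates and confounds, ordinary adjustment still removes the mediated part. The Expected Outcomes sentence states an expectation and specifies no model.

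Three stronger readings are tempting, and the documents support none of them:

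- *The sleep-adjusted coefficient is a direct effect.* Effect modification by sleep is expected and the measurement windows overlap, so one coefficient has no such clean meaning.
- *The sleep-free model gives the total effect.* It keeps ventilator-free days and sedative dose, which also accrue during the stay and may follow circadian disruption or delirium.
- *The two models always bracket the truth.* That follows from the signs chosen above and from giving earlier sleep no path of its own to delirium.

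The reach is also limited. Aims 1 and 2 are observational, and the randomised pilot is stated not to depend on them.

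**Conclusion.** The concern holds. The documents assign sleep disruption incompatible roles, and the single specified Aim 2 adjustment set conditions on a variable that the protocol's premise makes a mediator. On that premise the planned coefficient excludes the sleep-mediated part of the association, and a null result would not refute Hypothesis 2. This rests on the protocol's stated pathway and on the absence of any specified sleep-free model. The amount lost is unknown, and every figure below 1.12 or 1.08 depends on an assumed mediated share. Attenuation is likely if the premise is right, but not certain, because sleep may also confound. Aim 2 remains analysable, and the change should be made before the data are analysed.

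A smaller point: gender is among the controls in Expected Outcomes, and the Aim 2 analytic text says it is handled as in Aim 1, where models adjust for it. The Aim 2 model sentence omits it, probably by oversight.

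**What to change.** 1. Pre-specify an Aim 2 Poisson model without total sleep and overnight sleep efficiency. Keep age, severity of illness, ventilator-free days and sedative dose, and add gender. Use this model to address Hypothesis 2 as stated.
2. Report the planned model beside it, labelled a *sleep-adjusted association* and not a direct effect. Keep the sleep effect-modification tests with that model, since they need the sleep main effects.
3. State in advance that a null sleep-adjusted result alone does not refute Hypothesis 2, and that the sleep-free estimate may retain confounding if sleep also drives misalignment. State also that ventilator-free days and sedative dose accrue during the stay, so neither model is a clean total effect.
4. Reconcile the role of sleep across the central hypothesis, the premise for Aims 1 and 2, the Aim 2 Rationale and Expected Outcomes, and the Aim 2 analytic text including its covariate heading. Describe sleep as a hypothesised mediator that may also confound or modify, and say which model addresses which question.

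The cost is some wording and one additional fit on variables already collected. The downside is possible residual confounding in the sleep-free estimate, which is why both results should be shown.

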- a. **Setting:** The study site is the medical intensive care unit (MICU) at Yale-New Haven Hospital (YNHH), York Street Campus and St. Raphael's Campus. Median ICU stay is 3 days. Predominant reasons for admission are sepsis and acute respiratory failure. MICU rooms are private. There is currently a unit-wide sleep promotion protocol which limits care activities from 00:00 to 04:00.
- b. **Design:** Aim 1 and 2, prospective cohort study; Aim 3 pilot randomized controlled trial (RCT). Aim 3 which is not dependent on Aims 1 and 2 will be conducted first.
- c. **Cohort:** We will enroll 100 subjects at risk for ICU delirium. In addition, we will enroll 16 subjects into the pilot randomize control trial.
- d. **Inclusion and exclusion criteria:** This study will focus on adults at an increased risk for ICU delirium. We have selected age ≥ 50 years as an inclusion criteria to study middle-aged to older adults who are at increasing risk for delirium while not overly restricting our sample. We will not restrict patients based on admission severity of illness (APACHE II) because we think this is a critically important confounder and would like to study the effect of the full spectrum of severity of illness on our outcomes. We will exclude patients at significant risk for pre-existing circadian abnormalities (e.g. shift work). We will also exclude patients with co-morbid disease or medication use that makes measurement of urinary aMT6s or actigraphy unreliable. Table 2 lists inclusion and exclusion criteria.

Table 2: Inclusion Criteria	Exclusion Criteria

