 - i. **Actigraphy (Fig 3)** via the Actiwatch Spectrum™ (Philips Healthcare, Netherlands) set at 15-second epochs and placed on the patient's wrist will be used to measure rest-activity from enrollment until Study Day 5 or until MICU discharge. Actigraphy uses accelerometer technology mounted on a wristwatch-like device to characterizes rest versus activity of the wearer. This data device allows time series monitoring with a high sampling frequency and has been successfully used in the ICU

Figure 1: Actiwatch

setting.^{41, 42}

- ii. Heart rate varies around the clock with peaks in the late morning and early evening and a nadir during the sleep midpoint in normal patients.⁴³ Heart rate (5-second intervals) will be recorded per MICU standard of care from MICU admission until MICU discharge; this extended period of monitoring will provide insight into circadian abnormalities before study enrollment and after melatonin monitoring has been completed.

d. **Patient characteristics** for calculation of sleep midpoint, confounders, and effect modifiers will include collection of age, gender, sleep habits and timing, medical history (including hypertension and risk of obstructive sleep apnea (OSA) based on STOP-Bang Score⁴⁶), home medications, MICU admission diagnosis, sepsis presence and severity (as defined by the sepsis-3 criteria⁴⁷), illness severity (APACHE II score elements), ventilator support, and MICU medication use (including sedative-hypnotic medications). This data will be obtained via the EMR and via patient/surrogate interviews. Though the study is observational, melatonin, melatonin agonists, and non-benzodiazepine sleep aids (zolpidem, zopiclone, zaleplon) will not be given to study subjects while in the MICU. These agents are not part of usual care, and MICU leadership is agreeable to this restriction. ICU care events including phlebotomy, medication administration, transfusion, radiology studies, and procedures (e.g., line placement, intubation, endoscopy, catheterization, etc.) will be tracked by time of occurrence for the entire MICU admission. This process of obtaining timestamped care events has been automated via a collaboration with Yale ITS and requires minimal person-time.

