Aim 1 Analytical Approach: Individual sleep midpoint will be calculated as halfway between habitual bedtime and habitual waketime as indicated during patient/surrogate interview questionnaire. Light dose will be calculated as the sum of mean lux per hour for each hour between 08:00 and 17:00 (day dose) and 22:00 and 06:00 (overnight dose). A day/night dose ratio will then be calculated by dividing the daytime light dose by the overnight light dose. Light dose ratio will be treated as continuous exposure variables, with higher numbers indicating a more favorable (circadian) exposure and lower numbers indicating a less favorable (non-circadian) exposure. Circadian alignment and amplitude will be calculated using time series analysis of urinary aMT6s using smoothing techniques to examine characteristics of circadian rhythm: acrophase (maxima) and nadir (minima). Statistical measures will evaluate for serial correlation, seasonality (periodicity), and trend. Longitudinal cosinor techniques will be used to test for alignment of nadir and acrophase with normal circadian phase and amplitude (e.g., individual sleep midpoint and estimated normal peak aMT6s).⁵⁵ The degree of misalignment versus normal will be recorded in minutes. The amplitude of the cycle will be defined as one-half of the difference between the acrophase and nadir and will be recorded in nanograms (ng) per hour.³⁰ Normal values have been identified for aMT6s.^{30,56} The assessment of circadian abnormalities for association with light patterns will be solely based on aMT6s analysis. Heart rate, iButton gradient readings, and actigraphy activity counts will be evaluated via cosinor techniques analogous to the aMT6s analysis described above. Actigraphy activity counts will also be evaluated by visual inspection of normalized mean activity per hour (Fig 3) and as described by Duclos et al.³² Confounder and effect modifier variables: Severity of illness will be calculated according to the APACHE II algorithm⁵⁷ and expressed as a continuous variable. Sepsis will be expressed as a categorical variable (absent, septic, septic shock) based on the sepsis-3 criteria.⁴⁷ The risk of OSA will be expressed as a categorical variable (low risk, high risk) based on the STOP-BANG algorithm.^{46,58} Overnight ICU care events per the timestamp data described above will be calculated as the number of ICU care events per hour between 22:00 and 06:00. Average daytime and overnight room temperature will be calculated as a continuous variable.

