
Testing for Associations: Because both measures of circadian abnormality (misalignment and decreased amplitude) are continuous and normally distributed, multivariable linear regression models will test for associations, with light dose ratio serving as the exposure. Linearity of the associations will be examined graphically, and higher order terms will be considered as necessary. Models will be adjusted for age, gender, severity of illness, sepsis, risk of OSA, ICU care events per hour, and room temperature variables. We will test for modification of the association between light dose ratio and the outcomes by sepsis and risk of OSA. Because of the non-trivial intra-correlation coefficient expected from the serial correlation of the repeated outcome measures over time, models will employ generalized estimating equations with an auto-regressive correlation structure. Model fit will be evaluated with residual analysis, and significance will be defined as a two-sided p-value ≤ 0.05 . Power Calculations. For both continuous, normally distributed outcomes, power calculations assume a two-sided alpha of 0.05, power of 90%, a sample size of 100, and prevalence of covariates ranging from 20% to 50%. For minutes of misalignment, we further assume a mean of 180 minutes with a standard deviation of 95 and for amplitude a mean of 450 ng with standard deviation of 180.³⁰ Under these assumptions, our sample of 100 is sufficient to detect a range of minimal average shifts between 52-65 minutes of misalignment, and 98-123 ng of urinary aMT6 per

incremental change in the explanatory variables.

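### The Aim 2 delirium models omit sepsis, which the plan collects, codes and adjusts for in Aim 1; if sepsis prolongs delirium beyond the planned covariates, the circadian association will be confounded

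*Combined protocol and SAP*

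**What the plan says.** **Aim 2 model.** Under Statistical Considerations, Aim 2 Analytic Approach, Testing for Associations, the Poisson models relate misalignment and amplitude of aMT6s to days of delirium: "Models will be adjusted for age, severity of illness, ventilator-free days, dose of sedative medication, and measures of sleep disruption". Effect modification is tested "by age, sedative-hypnotic medication dose and measures of sleep disruption". The confounder paragraph just before carries over only three Aim 1 variables: "Severity of illness, age, and gender will be treated as in Aim 1". The Aim 2 Expected Outcomes paragraph lists age, gender, severity and ventilator-free days as controlled. Sepsis appears in none of these places.

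**Aim 1 model.** The corresponding sentence reads: "Models will be adjusted for age, gender, severity of illness, sepsis, risk of OSA, ICU care events per hour, and room temperature variables". Severity (APACHE II) and sepsis are separate terms there, and sepsis is also tested as an effect modifier.

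**Sepsis elsewhere in the plan.**
- Table 1 summarises a study of urinary aMT6s that found "abnormal aMT6s patterns in septic patients but not controls". The comparison groups were 7 non-septic ICU patients and 21 healthy people, against 17 septic patients.
- Project Overview, Setting: "Predominant reasons for admission are sepsis and acute respiratory failure". No percentage is given, and sepsis is not an exclusion criterion.
- Aim 1, Patient characteristics, includes "sepsis presence and severity (as defined by the sepsis-3 criteria" among the items collected. Aim 2 uses the same 100 subjects and the same patient data.
- Aim 1 Analytical Approach: "Sepsis will be expressed as a categorical variable (absent, septic, septic shock) based on the sepsis-3 criteria". No time point is attached to this status.

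**The concern.** In Aim 1 the aMT6s measures are the outcome; in Aim 2 they become the exposure. A variable that shifts aMT6s and also shifts delirium days is then a common cause of exposure and outcome, and leaving it out biases the coefficient of interest. The protocol itself supplies the first link, from sepsis to aMT6s. By entering sepsis next to APACHE II in Aim 1, it also shows that it does not regard the severity score as a full stand-in for sepsis where aMT6s is concerned. The second link, from sepsis to delirium days net of the planned covariates, is plausible, but the documents do not state it.

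Aim 2 is meant to ground later study of circadian entrainment as a treatment for delirium. If septic patients have both more disturbed aMT6s and more delirium days, the model could report an association when the circadian measure has no effect of its own, or enlarge a real one.

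**Working it through.** **Inputs from the plan.** Aim 2: n = 80, mean 3 days of delirium, overdispersion 20% (variance factor 1.2), two-sided alpha 0.05, power 90%. Aim 1: SD 180 ng for amplitude and 95 minutes for misalignment. Aim 2 gives no exposure SD, so using these is an assumption.

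**The plan's own figures.** It states minimal detectable ratios of 1.08 per 100 ng and 1.12 per 60 minutes.
- Amplitude: SE of the log ratio per 100 ng = sqrt(1.2 / (80 × 3)) / (180/100) = 0.0707 / 1.8 = 0.0393. Detectable ratio = exp((1.960 + 1.282) × 0.0393) = exp(0.127) = 1.136.
- Misalignment: SE = 0.0707 / (95/60) = 0.0447. Detectable ratio = exp(3.242 × 0.0447) = 1.156.

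Neither stated ratio is reproduced with the Aim 1 SDs, so both 1.08 and 1.136 serve as yardsticks below.

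**Size of the bias when the true amplitude effect is zero.** Assumptions, none given in the documents: proportion septic p = 0.5; amplitude lower in sepsis by d = 90 or 180 ng (0.5 or 1 SD) given the other covariates; sepsis-delirium ratio R = 1.25 or 1.5 net of those covariates.

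log ratio per 100 ng lower amplitude = ln(R) × d × p(1 − p) / 180² × 100

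For d = 90 and R = 1.25: 0.2231 × 90 × 0.25 / 32,400 × 100 = 0.0155, a ratio of 1.016. The false-positive rate is the chance that a normal variable with mean (log ratio / 0.0393) and SD 1 falls outside ±1.96.

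| d (ng) | R | log ratio | spurious ratio | false-positive rate |
|---|---|---|---|---|
| 90 | 1.25 | 0.0155 | 1.016 | 6.8% |
| 90 | 1.5 | 0.0282 | 1.029 | 11% |
| 180 | 1.25 | 0.0310 | 1.031 | 12% |
| 180 | 1.5 | 0.0563 | 1.058 | 30% |
| any | 1.0 | 0 | 1.000 | 5% |

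Against ln 1.08 = 0.0770 the bias is 20% to 73% of the effect the plan sets out to detect. Against 0.127 (the log of 1.136) it is 12% to 44%. With 30% septic, p(1 − p) = 0.21 and the spurious ratio runs from 1.013 to 1.048.

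**Does APACHE II adjustment remove it?** A simulation for misalignment used n = 80, mean 3 days, variance factor 1.2, a quasi-Poisson fit, 40% septic, and APACHE II 0.8 SD higher in sepsis and included in the model, with 1,500 runs per setting and no true circadian effect. Misalignment was 30 to 95 minutes greater in sepsis and R ran from 1.25 to 2.0.
- Without a sepsis term: spurious ratio 1.01 to 1.10 per 60 minutes, false-positive rate 6% to 48%.
- With a sepsis term: spurious ratio 0.998 to 1.004, false-positive rate about 4% to 6%.
- With R = 1.0: no bias, and about 5% in either model.

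**The case against.** The strongest reply is that half of the confounding argument is not in the documents. The Background lists critical-illness risk factors for delirium as severity of illness, ventilation and high-dose benzodiazepines. Sepsis is not named, and Aim 2 adjusts for all three, plus narcotics, propofol and dexmedetomidine. On that reading the Aim 2 set follows the protocol's own account of delirium, and Aim 1's use of sepsis shows only its relevance to aMT6s. This stands to the extent that different adjustment sets for different outcomes are not an inconsistency in themselves, and that any confounding would be residual. It does not settle the matter: the plan gives no reason for dropping a variable it ties to the Aim 2 exposure.

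The link to the exposure is also thinner than it looks. The Table 1 study is small and enrolled patients 11 days after ICU admission, whereas this cohort is enrolled within 30 hours of hospital admission. It reports abnormal patterns and does not say that amplitude is lower. The 90-180 ng gap is therefore an assumption, and 180 ng is 40% of the assumed mean of 450 ng.

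The arithmetic is not that of the planned model either. The closed form uses the marginal amplitude SD and the raw sepsis proportion. The simulation adjusts for APACHE II but not for ventilator-free days, sedatives or sleep. Patients delirious on the day of enrollment are excluded, and neither calculation asks whether the assumed sepsis ratio holds in those who remain. The 30% figure needs both upper assumptions together, and the 6.8% figure is barely above nominal. All of this stands, so the figures are illustrations.

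A reader might also infer that the case for the bright-light intervention falls with Aim 2. The documents do not support that: Project Overview, Design, says Aim 3 does not depend on Aims 1 and 2 and is run first.

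**Conclusion.** The omission is real and worth correcting. Sepsis is missing from every Aim 2 covariate list, although the protocol ties it to the Aim 2 exposure and already holds the data. The consequence is conditional: there is confounding only if sepsis adds delirium days beyond severity, ventilation and sedative dose. A reader might go further and conclude that an Aim 2 association would be due to sepsis, or that the true error rate is 7-30%. The documents support neither, because they give no sepsis-delirium effect, no sepsis prevalence and no amplitude difference.

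Under the assumptions shown, the bias ranges from slight to roughly half or more of the effect the study is designed to see, depending on the yardstick. If the net sepsis effect is nil, so is the bias. Because the remedy is cheap and the variable is in hand, the change should be made; confidence in the size of the problem is only moderate.

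**What to change.** Add sepsis (absent, septic, septic shock, as coded under Aim 1) to the Aim 2 adjustment sentence in Testing for Associations and to the Aim 2 confounder paragraph. Bring the controlled variables in the Aim 2 Expected Outcomes into line; gender, listed there and in the confounder paragraph but not in the adjustment sentence, can be reconciled at the same time.

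State when sepsis status is determined. Neither the data-collection text nor the coding text gives a time point. It should be fixed at or before enrollment, so that it precedes the 72 hours of aMT6s collection and cannot be a consequence of the exposure. If the omission is deliberate, give the reason and report the model with sepsis as a sensitivity analysis.

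Cost: a wording change and no new data. The model gains two parameters with about 80 patients and 80 × 3 = 240 expected delirium days, so some precision is lost in a model that already carries several drug-dose, sleep and interaction terms.
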